4.4 Post-Procedure Subject Management

Following the procedure, the subject will be treated in accordance with the hospital standard of care for PTCA interventions.

Sheath Removal and Ambulation

Use of approved vascular closure devices are allowed, provided the device is used according to the manufacturer's IFU and the operator has been properly trained in the device use. The subject may be ambulated according to hospital standards after hemostasis of the access site is achieved.

Medications

All subjects will be maintained on their routine therapeutic anticoagulation treatment or, in the absence of pre-existing treatment, subjects will receive a therapeutic daily dose of 75 mg of clopidogrel bisulfate (Plavix[®]) for a minimum of 6 months and aspirin \geq 75 mg to be taken throughout the length of the clinical investigation following index procedure.

If a subject develops hypersensitivity to clopidogrel bisulfate, they may be switched to ticlopidine hydrochloride at a dose in accordance with standard hospital practice.

Note: Subjects receiving ticlopidine hydrochloride must have a complete blood cell count (CBC) and differential blood count done per the IFU for ticlopidine hydrochloride.

4.5 Pre-Discharge Assessments

Medication History

The medication history should be updated as needed to include modifications to the chronic concomitant medications and protocol required medications.

Laboratory Tests

- Complete Blood Count
- Absolute Platelet Count
- Coagulation tests as per standard of care of the hospital (e.g., Prothrombin Time (PT) and activated Prothrombin Time (aPTT).

Cardiac Tests

- CK and/or CK-MB and cardiac troponin (cTn)
- 12 lead ECG

4.6 Subject Follow-up Post Hospital Discharge

Following hospital discharge, subjects will be followed at pre-determined time points during the study.

Subject Contact at 1 month $(30 \pm 7 \text{ days})$

Subjects will be contacted at 30 days post hospital discharge via phone call for assessment of overall condition, medications, physical questionnaire and adverse events. Alternatively, this contact can be performed in a site visit and include a physical examination. The physical questionnaire will include the following: arterial access site status, heart rate abnormalities, presence of elevated temperature, clinical events that

required a doctor's visit or hospital admission.

Subject Clinical Visit at 6 months (180 ± 30 days) according to the following sequence

- Physical examination
- 12 lead ECG
- Concomitant medication (name, dose, duration)
- Adverse event assessment
- Data regarding any emergent treatment and or serious adverse events and/or need for repeat angiography or interventions, and results of such if applicable
- Angiographic, IVUS or OCT follow-up per core laboratory guidelines for the subset of 25 subjects that has undergone these imaging procedures at index procedure.

Subject Clinical Visit at 12 months (365 \pm 30 days)

- Physical examination
- 12 lead ECG
- Concomitant medication (name, dose, duration)
- Adverse event assessment
- Data regarding any emergent treatment and or serious adverse events and/or need for repeat angiography or interventions, and results of such if applicable.

Subject Phone call follow up at 24 Months (730 \pm 30 days)

Subjects will be contacted at 24 months post hospital discharge via phone call for assessment of overall condition, physical questionnaire and medications. Alternatively, this contact can be performed in clinical visit with the referring physician.

Subject Phone call follow up at 36 Months (1095 \pm 30 days)

Subjects will be contacted at 36 months post hospital discharge via phone call for assessment of overall condition, physical questionnaire and medications. Alternatively, this contact can be performed in clinical visit with the referring physician.

PROCEDURE/TEST	Prior to Procedure	Pre-Procedure	Procedure	Pre-Discharge	30 days (± 7 days)	180 days (± 30 days)	1 year (± 30 days)	2 years (±28 days)	3 years (± 30 days)
Patient Medical History	X								
Review Inclusion/Exclusion Criteria ⁵	Х								
Patient Informed Consent	X								
Chronic Concomitant Medications/History	X	Х	Х	Х	X	X	Х	Х	Х
Creatinine	X								
CBC, Platelet Count	X			Х					
Coagulation Tests	X			Х					
Pregnancy Test (if applicable)	X								
CK-Mb		Х		Х					
Cardiac Troponin (cTn)		Х		Х					
12 Lead ECG ³		Х		Х		Х	Х		
Coronary angiogram			X ¹			X ²			
IVUS			X ⁶			X ⁶			
OCT			X ⁷			X ⁷			
Physical Examination	X				X ⁸	Х	Х		
Per-protocol medications		Х	Х	Х	X	Х	Х	Х	Х
Physical status q'naire					X ⁸			Х	Х
Adverse events ⁴			Х	Х	Х	Х	Х	Х	Х

Table 3. CVT-ISR Study Pre-Procedure, Procedural, Discharge and Follow Up Activities

1 Prior to and immediately post in-stent treatment with CVT Everolimus-coated PTCA Catheter.

2 In a subset of 25 patients at both index procedure and 180 day follow up

3 A 12 lead ECG will be performed within 24 hours post-procedure. Relevant copies of ECGs will be collected for death or any (suspected) myocardial infarction or (suspected) stent thrombosis that occurs after the index procedure for adjudication purposes by a Clinical Events Committee (CEC). This includes copies of the baseline ECG (screening and discharge) and event ECG (most abnormal ECG and last ECG recorded) if available.

4 AE collection will start when CVT Everolimus-coated PTCA Catheter has entered the vasculature.

5 A log of patients presenting to sites with in-stent restenosis be maintained and provide reasons for not including subjects in the study.

6. In a subset of 15 subjects at both index procedure and 180 day follow up

7. In a subset of 10 subjects at both index procedure and 180 day follow up

8. Depending on if the 30 day follow up is an office visit (exam) or phone call (questionnaire)

5. ADVERSE EVENTS

5.1 Adverse Events

At each evaluation, the investigator will determine whether any adverse events (AEs) have occurred. For the purpose of this protocol, an adverse event is any untoward medical occurrence, unintended disease or injury, or untoward clinical signs (including laboratory findings) in subjects, users or other person, whether or not related to the investigational medical device.

In this study, subjects should be encouraged to report AEs spontaneously or in response to general, non-directed questioning. If it is determined that an AE has occurred, the investigator should obtain all the information required to complete the AE Form of the CRF.

In addition, subjects will be instructed to contact the investigator, and/or study coordinator if any significant adverse events (e.g., MACE) occur between study evaluation visits.

AE collection will start when CVT Everolimus-coated PTCA Catheter has entered the vasculature.

Adverse events should be followed to resolution or stabilization, and if an ongoing AE changes in severity, a new AE entry for this event should be recorded. If a mild adverse event changes to a moderate or severe adverse event, the end date for the mild event and the start date for the moderate or severe event should be the same. Additionally, the mild event is considered resolved with the initiation of the moderate or severe event.

Adverse events that are present at the end of a subject's participation in the study should be marked as on-going on the case report form and the subject should receive posttreatment follow-up as appropriate.

5.2 Anticipated Adverse Events

An anticipated adverse event is any untoward medical occurrence in a subject that is predefined in the protocol and/or Instruction for Use (IFU) and that is identified or worsens during a clinical study, regardless whether or not the event is considered related to the study device or drug regimen prescribed as part of the protocol.

The following is a list of adverse events that may result from the PTCA procedure.

- Acute myocardial Infarction (Cardiac)
- Aneurysm
- Arrhythmias, including ventricular fibrillation (bradycardia & tachycardia)
- Arterial Dissection
- Arteriovenous fistula
- Bleeding
- Coronary artery spasm
- Coronary artery thrombosis
- Death (Cardiovascular or non-cardiovascular related)
- Discomfort during procedure

- Drug reactions or allergic reactions to contrast medium
- Distal Embolism (air, thrombus, plaque)/Device Embolism
- Endocarditis
- Fever
- Groin bruising/discomfort
- Hematoma
- Hemorrhage
- Hypotension/hypertension
- Injury at blood vessel access site requiring surgical or medical treatment
- Ischemia
- Pseudoaneurysm
- Renal failure
- Restenosis of the dilated vessel
- Sepsis, infection
- Stroke or cerebrovascular event
- Total occlusion of the coronary artery or bypass graft
- Unstable angina
- Vessel dissection, perforation, rupture or injury
- Thrombosis
- Vomiting/Nausea

The oral formulation of everolimus has been evaluated in clinical trials and is approved worldwide for the prophylaxis of organ rejection in adult kidney transplant recipients at low-moderate immunologic risk and for the treatment of patients with advanced renal cell carcinoma. Oral dose of everolimus depending on the indication ranges between 1.5 and 20 mg/day. The following list includes the known risks of everolimus at these oral doses. *The following is a list of theoretical adverse events that may result from the addition of everolimus to a PTCA catheter:*

- Abdominal pain
- Anemia
- Angioedema
- Anorexia
- Asthenia
- Constipation
- Cough
- Delayed wound healing/fluid accumulation
- Diarrhea
- Dyslipidemia (including hyperlipidemia and hypercholesterolemia)
- Dyspnea
- Dysgeusia
- Dyspepsia

- Dysuria
- Dry skin
- Edema (peripheral)
- Epistaxis
- Fatigue
- Headache
- Hematuria
- Hyperglycemia
- Hyperlipidemia
- Hyperkalemia
- Hypertension
- Hypokalemia
- Hypomagnesemia
- Hypophosphatemia
- Increased serum creatinine
- Infections and serious infections: bacterial, viral, fungal, and protozoal infections
- Insomnia
- Interaction with strong inhibitors and inducers of CYP3A4 or PgP
- Leukopenia
- Lymphoma and other malignancies (including skin cancer)
- Male infertility
- Mucosal inflammation (including oral ulceration and oral mucositis)
- Nausea
- Neutropenia
- Non-infectious pneumonitis
- Pain: extremity, incision site and procedural, and back
- Proteinuria
- Pruritus
- Pyrexia
- Rash
- Stomatitis
- Thrombocytopenia
- Thrombotic microangiopathy
- Thrombotic thrombocytopenic purpura
- Tremor
- Urinary tract infection
- Upper respiratory tract infection
- Vomiting

The following is a list of adverse events that may result from the follow-up angiography

procedures:

- Acute myocardial Infarction
- Arrhythmias, including ventricular fibrillation (bradycardia & tachycardia)
- Arteriovenous fistula
- Coronary artery spasm
- Death (Cardiovascular or non-cardiovascular related)
- Drug reactions or allergic reactions to contrast medium
- Hematoma (Access Site Complication or Bleeding)
- Hypotension/hypertension
- Infection (Access Site Complication)
- Pain and tenderness
- Pseudoaneurysm
- Restenosis of the dilated vessel
- Stroke, air embolism, and embolization or fragmentation of thrombotic or atherosclerotic material (Neurologic)
- Total occlusion of the coronary artery or bypass graft
- Unstable angina
- Vessel dissection, perforation, rupture or injury

5.3 Adverse Event Severity

The investigator will use the following definitions to rate the severity of each adverse event:

Mild	Awareness of a sign or symptom that does not interfere with the subject's usual activity or is transient, resolved without treatment and with no sequelae
Moderate	Interferes with the subject's usual activity and/or requires symptomatic treatment
Severe	Symptom(s) causing severe discomfort and significant impact of the subject's usual activity and requires treatment

5.4 Relationship to Study Device

The investigator will use the following definitions to assess the relationship of the adverse event to the use of study device:

Not Related	 Relationship to the device or procedures can be excluded when: The event has no temporal relationship with the use of the investigational device or the procedures related to the application of the investigational device. The serious adverse event does not follow a known response pattern and is biologically impossible. The discontinuation of medical device application or the reduction of the level or activation/exposure, when clinically feasible, and the re-introduction of its use do not impact on the serious adverse event. The event involves a body-site or an organ that cannot be affected by the device or procedure. The serious adverse event can be attributed to another cause (e.g. an underlying or concurrent illness/clinical condition, an effect of another device/drug/treatment, or other risk factors). The event does not depend on a false result given by the investigational device used for diagnosis, when applicable.
Possible	The relationship with the use of the investigational device or the relationship with procedures is weak but cannot be ruled out completely. Alternative causes are also possible (e.g. an underlying or concurrent illness/clinical condition, an effect of another device/drug/treatment). Cases where relatedness cannot be assessed, or no information has been obtained, should be also be classified as possible.
Probable	The relationship with the investigational device or the relationship with the procedures seems relevant and/or the event cannot be reasonably explained by another cause.
Highly Probable	 The serious adverse event is associated with the investigational device or with procedures beyond reasonable doubt when: The event is a known side effect of the product category the device belongs to or of similar devices and procedures. The event has a temporal relationship with the investigational device use/application or procedures. The event involves a body-site or organ that a) the investigational device or procedures are applied to or b) the investigational device or procedures have an effect on. The serious adverse event follows a known response pattern to the medical device. The discontinuation of the medical device application (or reduction of its use (or increase in the level of activation/exposure) and reintroduction of its use (or increase in the level of activation/exposure) impact on the serious adverse event

(when clinically feasible).
• Other possible causes (e.g. an underlying or concurrent illness/critical condition or/and an effect of another device, drug or treatment) have been adequately ruled out
• Harm to the subject is due to error in use.
• The event depends on a false result given by the
investigational device used for diagnosis, when applicable.

5.5 Serious Adverse Events

An Adverse Event is considered serious if the event led, or might have led, to one of the following outcomes:

- Death of a subject
- Serious deterioration in the health of a subject that resulted in any of the following:
 - o Life-threatening illness or injury
 - Permanent impairment of a body structure or body function
 - o Hospitalization or prolongation of patient hospitalization
 - Medical or surgical intervention to prevent life-threatening illness or injury or permanent impairment to a body structure or body function
 - Chronic disease
- Foetal distress, foetal death or a congenital physical or mental impairment or birth defect

Planned hospitalizations for pre-existing conditions or a procedure required by this protocol without serious deterioration in health is not considered a serious adverse event.

5.6 Procedures for Reporting Serious Adverse Event

Criteria for Reporting Serious Adverse Event

Serious adverse events are required to be reported for the following situations:

- a. Any serious adverse event that has a causal relationship with the investigational device or the investigation procedure or where such as causal relationship is reasonably possible.
- b. Any device deficiency that might have led to a serious adverse event if appropriate action had not been taken, intervention had not occurred or circumstances had been less fortunate.
- c. Any new findings in relation to any event referred to in points (a) and (b) above.

Reporting by the Sponsor to National Competent Authorities

The Sponsor must report serious adverse events to the National Competent Authorities (NCAs) where the clinical investigation has commenced per the following timelines:

• For all reportable events which indicate an imminent risk of death, serious injury or serious illness and that requires prompt remedial action for other subjects, users

or other persons or a new finding to the event: *Immediately but not later than two* (2) calendar days after awareness by the Sponsor of a new reportable event or of new information in relation with an already reported event.

• For other reportable events or a new finding/update: *Immediately but not later than seven (7) calendar days following the date of awareness by the sponsor of the new reportable event or of new information in relation with an already report event.*

Reporting by the Clinical Trial Investigator to Sponsor

The Clinical Trial Investigator will report to the Sponsor immediately but no later than three (3) calendar days after investigational site study personnel become aware of the event.

Risk Assessment

In conjunction with the Coordinating Clinical Investigator and/or, if need be, the Clinical Event Committee (section 10.2) the Sponsor shall decide whether, as a result of a serious adverse event, the safety of study participants is at risk, or whether continuation of the trial is in jeopardy.

Corrective Measures

If any situation potentially jeopardizing the safety of subjects, users or third persons arise during a clinical trial or approved performance evaluation, then the Sponsor and those persons carrying out the clinical trial or the performance evaluation shall immediately take all of the essential safety measures in order to protect subjects, users or third persons from direct or indirect danger. The Sponsor or his representative shall immediately inform the competent Authority and arrange for the competent Ethics Committee to be informed of the latest developments.

6. STATISTICAL DESIGN AND ANALYSIS

6.1 Statistical Overview of the Trial

The primary sample size calculation is based on the hypotheses that the primary safety and effectiveness endpoints meet *a priori* specified Objective Performance Criteria (OPC).

The OPCs for the primary safety endpoint and effectiveness endpoints have been set using historical control data from thirty-two (32) published studies that evaluate treatments for ISR, analyzed in meta-analysis and also reviewed in a consensus document⁶. Since this is a feasibility trial, the attainment of statistical significance is neither a necessary nor a sufficient condition for determine whether the device merits further study. If the data exhibit a trend ($p \le 0.10$) toward statistical significance when compared to historical control and raise no safety concerns, it may be deemed worthy of further investigation. In addition, there will be a focus on estimating the magnitude of observed values at 180 days post-procedure and their associated 90% confidence

⁶ Jeger et al. Third International DCB Consensus Group Report JACC: Cardiovascular Interventions, 2020June;1 3(12):1391-402 Ae-Young Her et al. Current Management of In-Stent Restenosis, Korean Circ J. 2018 May;48(5):337-349 Leos Pleva et al. Treatment of coronary in-stent restenosis: a systematic review *J Geriatr Cardiol* 2018; 15: 173-184

intervals.

6.2 Analysis Populations

The primary endpoints will be analyzed on the entire safety population and on the evaluable subject population, as appropriate.

The safety population will consist of all subjects who enrolled into the trial and for whom the procedure had been initiated.

All effectiveness endpoints will be analyzed using the evaluable population, which consists of subjects who had no bailout and at least one valid follow-up visit.

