3.4 Other Clinical Endpoints

³ Garcia-Garcia HM, McFadden EP, Farb A, et al. Standardized End Point Definitions for Coronary Intervention Trials: The Academic Research Consortium-2 Consensus Document. Circulation. 2018;137(24):2635-2650. doi:10.1161/CIRCULATIONAHA.117.029289

⁴ Moussa ID, Klein LW, Shah B, et al. Consideration of a new definition of clinically relevant myocardial infarction after coronary revascularization: an expert consensus document from the Society for Cardiovascular Angiography and Interventions (SCAI). J Am Coll Cardiol. 2013;62(17):1563-1570. doi:10.1016/j.jacc.2013.08.720

- Target lesion failure (TLF) at 30 days, 1, 2 and 3 years, post-procedure, defined as a composite rate of cardiovascular death, target vessel myocardial infarction and clinically-driven target lesion revascularization (TLR).
- Target vessel failure (TVF) at 30 days, 180 days and 1, 2 and 3 years post-procedure, defined as a composite rate of cardiovascular death, target vessel myocardial infarction, and target vessel revascularization (TVR).
- Clinically-driven target lesion revascularization (TLR) at 1, 2 and 3 years post-procedure.
- Clinically-driven target vessel revascularization (TVR) at 180 days and 1, 2 and 3 years post-procedure.
- Rate of vascular access site complication, defined as the combined rate of hematoma, AV fistula or a pseudoaneurysm that required intervention, such as surgical repair or transfusion, prolonged hospital stay or required a new hospital admission.
- Lesion success (per device), defined as achievement of a final in-lesion residual diameter stenosis of <30% (by QCA), using any device after wire passage through the lesion. Pre- and post-dilatation of the lesion with a non-study device is considered part of assigned device treatment.
- Technical success (per device), defined as achievement of a final in-lesion residual diameter stenosis of <30% (by QCA), using the CVT Everolimus-coated PTCA Catheter without a device malfunction after wire passage through the lesion. Pre- and post-dilatation are considered part of assigned device treatment.
- Clinical success (per subject) defined as technical success without the occurrence of major adverse events during the procedure.
- Procedural success (per subject) defined as lesion success without the occurrence of major adverse events during the procedure.

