Record an image of the target lesion after pre-dilatation is completed. Ensure to perform an angiography distal to the target lesion. Assess the subject for any angiographic complications after pre-dilatation and confirm the lesion to be treated meets the study angiographic inclusion and exclusion criteria.

Successful pre-dilatation of the target lesion is defined as:

- Residual stenosis of <30% after pre-dilatation (per visual estimate) AND
- No major (>Grade B) flow-limiting dissection.

In case of unsuccessful pre-dilatation of the target lesion planned to be treated with the investigational device, the subject should be considered a screen failure and all lesions should be treated as per standard of care.

Treatment with CVT Everolimus-coated Catheter

It is recommended to select a CVT EVE-PTCA Catheter with a balloon length that allows for coverage of the targeted lesion plus approximately 2 mm additional coverage, by visual estimate, on each side of the lesion while not allowing the balloon length extend beyond the edges of the stent.

The balloon should be inflated for 60 seconds in order to allow for an optimal drug delivery to the surrounding tissue.

Post-Procedure Angiography Subset

A subset of twenty-five (25) subjects will complete post-procedure angiography assessment of the target vessel, as per the angiographic core laboratory guidelines, at 6 months post-procedure.

The 25 subjects undergoing angiographic follow up will represent the first subjects enrolled into the study, with no more than 15 patients undergoing angiographic follow up from a single site.

Note: The end of the procedure is defined as the time after a complete final angiogram has been performed and the last guidewire and catheter have been removed. In case the subject needs to return to the procedure room and a guiding catheter is reinserted for dilatation, this is considered a reintervention. Removal of the sheath(s) may be done at the Investigators discretion.

All catheters, including the CVT Everolimus-coated PTCA Catheter, should be delivered and deployed per their respective Instructions for Use (reference Appendix E for CVT Everolimus-coated PTCA Catheter IFU). All balloon inflations should be captured per the angiographic core laboratory guidelines.

Intravascular Ultrasound Examination (IVUS)

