Adjunctive therapies should be avoided if possible. In case of suboptimal procedure results (>50 % residual stenosis, perforation, occlusive complication (recoil) or flow limiting dissection) prolonged balloon inflation should be attempted. If a subject in this study experiences a major dissection or an occlusive complication (as evidenced by decreased target vessel flow, chest pain, or ischemic electrocardiogram (ECG) changes which do not respond to standard rescue techniques), bailout stenting procedures may be performed. All other adjunctive therapies (including but not limited to: laser, atherectomy, cryoplasty or brachytherapy) are not allowed.

If bailout procedures are performed, justification should be documented on the CRF. Subjects undergoing bailout procedures will continue in the study and their data will remain part of the statistical analyses.

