 - \circ Standard deviation is assumed to be 0.5 mm in the treatment group.
- Two-tailed α =0.10

Given the above assumptions, enrolling 25 subjects (analysis of 25 evaluable subjects) will provide 87% power for demonstrating CVT treatment's superiority over historical controls in LLL.

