6.4 Statistical Analyses

Detailed analyses of the primary endpoints will be performed when all of the subjects complete their primary follow-up visit at 180 days. No effort will be made to impute or extrapolate data to replace missing values. All calculations will be based on available data with missing data excluded.

Analysis of Primary Endpoints

The primary safety endpoint of freedom from target lesion failure (TLF) rate at 6 months post-index procedure will be analyzed using the safety population.

The analysis of the primary effectiveness endpoint of LLL at 6 months will utilize the evaluable populations.

Analysis of Secondary Endpoints

All secondary endpoints will be analyzed using descriptive statistics.

For binary variables, such as technical success counts, percentages and exact 95% confidence intervals using Clopper-Pearson's method will be calculated. For continuous variables, means, standard deviations, and 95% confidence intervals for the mean using the Gaussian approximation will be calculated. If the assumption of normality seems untenable, nonparametric methods will be employed instead.

For time-to-event variables, such as time to target lesion revascularization, survival curves will be constructed using Kaplan-Meier estimates.

Analysis of Other Data

The clinical laboratory values collected will be analyzed by tabulating the number and percentage of subjects with clinically significant changes from baseline for each parameter at each time point.

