Undetermined. It is defined as a death not attributable to any other category because of the absence of any relevant source documents. Such deaths will be classified as cardiovascular for end point determination.

Device Malfunction

A malfunction is a failure of a device to meet its performance specifications or otherwise perform as intended. Performance specifications include all claims made in the labeling of the device. The intended performance of a device refers to the intended use for which the device is labeled

Dissection Grades

National Heart, Lung, and Blood Institute (NHLBI) Dissection Classification System: (0, A, B, C, D, E, F)

- 0: No dissection
- A Minor radiolucent areas in the lumen without impairment of flow or persistent dye staining after contrast runoff
- B Luminal flap that is radiolucent and that runs parallel to the vessel wall with contrast injection but without impairment of flow or persistent dye staining after contrast runoff
- C: Contrast appears outside of the vessel lumen as an "extra-luminal cap". The staining appears even after contrast clears the lumen
- D: Spiral radiolucent luminal filling defects. Often persistent staining after contrast clears from the vessel.
- E: New and persistent filling defects in the vessel lumen.
- F: Lesions that progress to impaired flow or total occlusion.

Embolism

Formation of a thrombus within the target lesion with migration or atherosclerotic emboli migration to a distal artery.

Hematoma

A localized collection of blood in a space or tissue.

Intent-to-Treat (ITT) Population

The principle of including outcomes of all patients in the analysis who are enrolled into the clinical trial/investigation, regardless of the treatment actually received.

Late Lumen Loss (LLL)

Calculated as Minimum Lumen Diameter (MLD) post-procedure - MLD at follow-up

Mean in-lesion Late Loss will also be measured: (Mean In-lesion MLD, post-procedure) – (Mean In-lesion MLD at follow-up)

Lead Principal Investigator

A physician-specialist, related to the study, which is responsible for the overall conduct of the trial at all sites.

Major Adverse Cardiac Event (MACE)

Death, myocardial infarction (Q wave and non-Q wave), emergent coronary bypass surgery, or clinically driven repeat target lesion revascularization by percutaneous or surgical methods.

Minimum Lumen Diameter (MLD)

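### Subjects who need bailout are dropped from the primary LLL analysis although section 4.3 keeps their data, and the success endpoints have no named population and, for technical and clinical success, no rule for scoring a bailout stent

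*Combined protocol and SAP*

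**What the plan says.** Section 6.2 sets the effectiveness population: "All effectiveness endpoints will be analyzed using the evaluable population, which consists of subjects who had no bailout" and who also have at least one valid follow-up visit. Section 6.4 repeats it for the primary endpoint: "The analysis of the primary effectiveness endpoint of LLL at 6 months will utilize the evaluable populations". The safety population in 6.2 is everyone enrolled whose procedure was started, bailout or not, and 6.4 uses it for target lesion failure (TLF).

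Section 4.3, under the bail-out criteria, gives a general rule with no endpoint excepted: "Subjects undergoing bailout procedures will continue in the study and their data will remain part of the statistical analyses". It adds: "If bailout procedures are performed, justification should be documented on the CRF".

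Appendix B defines an intent-to-treat population as "The principle of including outcomes of all patients in the analysis who are enrolled into the clinical trial/investigation, regardless of the treatment actually received". Section 6 assigns no analysis to it.

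Section 3.4 lists lesion, technical, clinical and procedural success among the other clinical endpoints. Lesion success is "achievement of a final in-lesion residual diameter stenosis of <30% (by QCA), using any device after wire passage through the lesion", and procedural success builds on it. Technical success requires the study catheter without malfunction and names only pre- and post-dilatation as part of treatment. Clinical success builds on technical success. Section 6.4 gives technical success as an example of a binary variable to be reported with an exact 95% interval, but names no population.

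**The concern.** Under 3.10 a subject is enrolled only after successful pre-treatment and once the study catheter has entered the vasculature. Under 4.3 a failed pre-dilatation is a screen failure. A bailout therefore happens to a subject already enrolled, and it marks a poor or complicated acute result. Removing these subjects from LLL conditions effectiveness on that result having been good.

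This is a first-in-human study of a balloon (9.6), so how often it needs a rescue stent is a basic result. No bailout rate is among the planned endpoints. Stenting in the index session is not by itself a TLF, because Appendix B defines target lesion revascularization as a repeat intervention. The success endpoints are where bailout would be expected to appear, and their denominator is not fixed. For technical and clinical success the numerator is not fixed either, so the rate could be settled after the data are seen.

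**Working it through.** **1. Text side by side**

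| Endpoint | Population named? | Bailout stent handled? |
|---|---|---|
| TLF at 6 months | Safety (6.4) | Subject kept; agrees with 4.3 |
| Primary LLL | Evaluable (6.2, 6.4) | Subject excluded; conflicts with 4.3 |
| Lesion, procedural success | None | Any-device wording: a stented lesion below 30% stenosis counts, and procedural success also needs no major adverse event |
| Technical, clinical success | None | Not stated |

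**2. Inputs**

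From the plan:
- 50 subjects, 25 of them imaged
- control LLL 0.80 mm, treatment LLL 0.30 mm, SD 0.5 mm, two-sided alpha 0.10 (6.3)
- 90% intervals (6.1) and exact 95% intervals for binary secondary endpoints (6.4)

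Assumed, because the documents give no bailout rate:
- 1 to 5 bailouts in 50, one device per subject, no other failure
- for LLL, k = 1 to 3 bailouts among the 25 imaged, with LLL d = 0.25 to 1.0 mm above 0.30 mm
- as a harder case, k = 5 of 25 with bailout LLL of 0.8 to 1.2 mm (d = 0.5 to 0.9)

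**3. The plan's own figure.** The only stated number tied to the evaluable population is in 6.3: "enrolling 25 subjects (analysis of 25 evaluable subjects) will provide 87% power". A one-sample t test with the stated inputs has noncentrality 0.50/(0.5/√25) = 5 and power 99.9%, so 87% does not reproduce. That is a separate matter. With 5 of the 25 excluded, n = 20 and power is 99.6%, so the exclusion does not threaten power.

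**4. Technical success.** Exact 95% limits for x of n are the 0.025 quantile of Beta(x, n−x+1) and the 0.975 quantile of Beta(x+1, n−x).

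| Bailouts | Bailout = failure, safety population | Bailouts excluded (6.2 read to apply) |
|---|---|---|
| 1 | 49/50 = 98% (89.4% to 99.9%) | 49/49 = 100% (92.7% to 100%) |
| 5 | 45/50 = 90% (78.2% to 96.7%) | 45/45 = 100% (92.1% to 100%) |

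If 6.2 does not apply and a stented result is accepted as a technical success, 5 bailouts give 50/50 = 100% (92.9% to 100%). If 6.2 does apply, its follow-up condition also removes a subject who dies before any follow-up visit, from all four success denominators.

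**5. LLL**

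The mean with bailouts included is 0.30 + k·d/25.
- k = 1, d = 0.25: shift 0.01 mm
- k = 2, d = 0.5: shift 0.04 mm
- k = 3, d = 1.0: shift 0.12 mm

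The 90% half-width at n = 25 is t(0.95; 24) × 0.5/5 = 1.711 × 0.1 = 0.17 mm, larger than any of these.

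Upper 90% limit, bailouts excluded: 0.30 + t × 0.5/√n = 0.475 mm at n = 24 and 0.483 mm at n = 22.

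Upper 90% limit, bailouts included: total SD = √[(24 × 0.25 + k(25−k)/25 × d²)/24], and the limit is the mean + 1.711 × SD/5.
- k = 1, d = 0.25: SD 0.50, limit 0.48 mm
- k = 3, d = 1.0: SD 0.60, limit 0.42 + 0.205 = 0.63 mm
- k = 5, d = 0.5 to 0.9: mean 0.40 to 0.48 mm, SD 0.54 to 0.62, limit 0.58 to 0.69 mm

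Every limit is below 0.80 mm.

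**The case against.** Section 4.3 can be read loosely: the data remain in the analyses because the safety population keeps these subjects for TLF, and 6.2 is the more specific rule for effectiveness. That reading is possible but not written. The opening of 6.2, which assigns the primary endpoints to the safety and evaluable populations as appropriate, does not help, because 6.4 sends LLL to the evaluable set alone.

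Reading 6.2 to cover the success endpoints is the weaker reading. They are listed as other clinical endpoints, 6.4 treats technical success as secondary, and a follow-up condition makes little sense for an acute outcome. This stands: the 100% figures with bailouts excluded show what the text leaves open, not what it prescribes. The contrast between lesion and technical success also suggests that a stented result is not a technical success, but 3.4 does not say so.

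Excluding bailouts from LLL has a rationale. The instructions for use name a bare metal stent for bailout, so LLL would then reflect balloon plus stent. This also stands, and it is why that analysis should be kept. Screening out failed pre-dilatations should make bailouts fewer.

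A reader might infer that none of the four success endpoints deals with bailout. The any-device wording settles lesion and procedural success. A reader might also infer that bailout subjects in the 25 have invasive imaging for nothing. That would require 6.2 to reach the further imaging endpoints in 3.5, which no text labels as effectiveness endpoints. Nor would bailouts be hidden: the CRF and adverse event data would show them, and 6.1 makes the absence of safety concerns a condition for going further.

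**Conclusion.** The concern holds in limited form. Section 6.2, applied by 6.4, removes enrolled bailout subjects from primary LLL, contrary to the unqualified sentence in 4.3, and so selects on an outcome of treatment. No success endpoint has a named population, technical and clinical success lack a rule for a bailout stent, and no bailout rate is planned.

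The main effect is on the descriptive success rates: 2 percentage points in technical success with 1 bailout in 50, and 10 points with 5. A reader might infer that the LLL result is in doubt or the study underpowered; the arithmetic does not support either. All sizes rest on assumed bailout counts, one device per subject, no other failure and assumed LLL after bailout. The contradiction and the gaps in the text do not depend on those assumptions.

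**What to change.** 1. In 6.2, state that lesion, technical, clinical and procedural success are analysed in the safety population, with no exclusion for bailout or missing follow-up.
2. In 3.4, state that bailout stenting is a technical failure and therefore a clinical failure.
3. Report the bailout stenting count and percentage with the exact 95% interval that 6.4 already uses. For example, 1/50 = 2% (0.1% to 10.6%) or 5/50 = 10% (3.3% to 21.8%).
4. Keep the no-bailout LLL analysis, and add LLL in all subjects with 180-day angiography, bailouts included, as a sensitivity analysis.
5. Cross-reference 4.3 to 6.2 so that the bailout sentence says which analyses keep these subjects.

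The cost is wording in three sections and one or two tables, with no change to sample size or visits. The Procedural Form in Appendix L already records treatment for dissection and stent type. Stents placed for other reasons can be counted from the bailout justification that 4.3 requires. The downside is a possibly slightly less favourable success rate or LLL.
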